## Informed consent procedure:

[figure not shown]
All patients with capacity will be asked to provide a prospective written informed consent (See Appendix 3). For patients without capacity, a deferred consent procedure will take a place. In this case, an independent clinician will review and sign that the patient is lacking capacity and he/she fulfils all criteria to be enrolled to the

Unique Protocol ID: 2021-002290-25 22.9.2021 Protocol version 9.2

study. The patient's next of kin will be informed about the study as soon as practical with the aid of information leaflet (Appendix 3). The patient will be asked to provide and sign informed consent as soon as he/she regains the capacity to do so. In case of consent refusal, patient's data will not be used in per-protocol analysis.

22.9.2021 Protocol version 9.2

#### Procedures at baseline:

#### Day 0

In patients with diarhea, after confirmation of negative pregnancy test in fertile women informed consent will be subscribed. The drug chart will be reviewed and all medication that can be contributing to diarhea will be stopped if it is considered safe to do so. Abdominal X ray will be performed to rule out pneumoperitoneum or megacolon. After obtaining baseline stool sample (sent for study analyses but also for GDH, C. dif. toxins A and B and faecal calprotectin), blood sample will be tested for standard tests ( biochemistry, blood count, etc.). Stool and plasma samples will be frozen at -80 C for later analysis.

Randomisation will be performed by sealed envelope in the evening of day No.0. Enteral nutrition will be stopped at 18:00 at the latest.

### Day 1

The patient will be physically examined in the morning, including the determination of the degree of SOFA score (a set of laboratory results and examinations estimating organ function). Stool and plasma samples will be frozen at -80 C for later analysis. The frequency, amount and structure of the patient's stools will be recorded. Patients will be treated for their primary disease throughout the study according to established standard procedures.

In both groups adequate hydratation will be taken care of by replacing the fluids lost by diarrhea with infusion. Throughout the treatment, we monitor the patient's vital functions (body temperature, heart rate, blood pressure, blood oxygen saturation)

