#### Sample study size:

We plan to randomise 36 patients in 1:1 ratio: This is a pilot trial, with primary outcome being feasibility and safety of faecal bacterial transplantation in the population of critically ill adults with C. dif. positivity and diarrhoea. However, with 36 randomised patients, the study will have sufficient power to determine non-inferiority against standard-of-care based on data available in FBT in patients with C. dif. In two trials in non-critically ill patients, the success of FBT was 69% (22 out of 32) or 56% (5 out of 9) as compared to 45% cured by oral metronidazole. Assuming that clinically significant difference between the two methods is 20% and the intervention will be as effective in ICU patients as it was in the non-critically ill group (curing 27 out of 41, ie. 66%), if there is a true difference in favour of the experimental treatment of 21%, then 36 patients are required to be 80% sure that the upper limit of a one-sided 95% confidence interval (or equivalently a 90% two-sided confidence interval) will exclude a difference in favour of the standard group of more than 20%. The expected duration of participation in the study is 6 months.

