# Statistical plan:

Safety parameters will be reported on intention-to-treat basis. Primary outcome will be compared by as unadjusted hazard ratio of not being cured (with 95% interval) in a per protocol analysis. The subset of patients with C. dif positivity will be analysed separately.

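### No stratification by C. dif. status is described and the primary comparison is unadjusted, although that status sets the treatment in both arms and defines separate analyses

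*Combined protocol and SAP*

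**What the plan says.** **Allocation.** Under Sample study size: "We plan to randomise 36 patients in 1:1 ratio". Under Procedures at baseline, Day 0: "Randomisation will be performed by sealed envelope in the evening of day No.0". Nothing further is said about how the sequence is generated.

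**Testing.** Also under Day 0, the baseline stool sample is "sent for study analyses but also for GDH, C. dif. toxins A and B and faecal calprotectin". The time at which the result returns is not stated.

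**Treatment by status.** Under Control group, C. dif.-positive patients receive vancomycin and the others wait for the diarrhoea to resolve. Under Intervention group, positive patients have a saline enema at the time of diagnosis and a repeat FBT; the others have one FBT.

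**Analysis by status.** Secondary end-points lists a positive versus negative subgroup analysis. The Statistical plan adds: "The subset of patients with C. dif positivity will be analysed separately". The same section gives the primary comparison as unadjusted.

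**Population.** C. dif. positivity is not an inclusion criterion under Study subjects, so the entry criteria admit both kinds of patient. The share expected to be positive is not given.

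**The concern.** The trial pools two contrasts: FBT against waiting in C. dif.-negative patients, and repeated FBT against an active drug in C. dif.-positive patients. The factor that separates them is tested at baseline, but neither the described allocation nor the primary analysis uses it. In 36 patients, chance alone can put noticeably more positives in one arm. If cure at day 7 differs by C. dif. status, part of the observed difference between arms then reflects case mix, and an unadjusted comparison does not remove it. The separate C. dif. analysis can also be left with a lopsided split, such as 6 against 2.

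**Working it through.** **1. The plan's own sample size.** Inputs from Sample study size: control cure 45%, FBT cure 66% (27/41), margin 20 points, one-sided 5%, power 80%. With unpooled variance,

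n per arm = (1.645 + 0.842)² × (0.45×0.55 + 0.66×0.34) / (0.21 + 0.20)² = 17.4, rounded up to 18.

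This gives 36 in total, as stated. At 18 per arm the standard error of the difference is √(0.2475/18 + 0.2244/18) = 0.162, and power is Φ(0.41/0.162 − 1.645) = 81.3%.

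**2. Chance of imbalance.** Assumptions: arms of exactly 18; K positives among the 36, with K from 6 to 16; no stratification. The number X of positives in the FBT arm is hypergeometric (36, K, 18), and the arm difference is D = 2X − K. For K = 12:

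P(|D| ≥ 4) = 2 × P(X ≤ 4) = 2 × 180,859,770 / 1,251,677,700 = 0.289.

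| K (even) | P(\|D\| ≥ 4) | K (odd) | P(\|D\| ≥ 4) |
|---|---|---|---|
| 6 | 17.7% | 7 | 8.8% |
| 8 | 22.8% | 9 | 12.1% |
| 10 | 26.4% | 11 | 14.6% |
| 12 | 28.9% | 13 | 16.4% |
| 14 | 30.5% | 15 | 17.6% |
| 16 | 31.5% | | |

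When K is odd, D is odd, so four or more means five or more; that is why the odd column is lower. Beyond the assumed range, the probability is 32% at K = 18, 29% at K = 24 and 18% at K = 30.

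**3. Effect on the primary difference.** Four patients are 4/18 = 22.2 points of prevalence. If cure differs between C. dif. strata by the same amount in both arms, the shift is 0.222 × gap: 4.4 points for a gap of 20 and 8.9 points for a gap of 40. For odd K the smallest qualifying difference is five, which gives 5/18 × gap, or 5.6 to 11.1 points. The gap is an assumption, and the shift can favour either arm.

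**4. Typical shift.** The SD of the between-arm difference in share positive is √(K(36 − K)/35)/18. This is 12.6 points at K = 6 and 16.8 points at K = 16. Multiplied by a gap of 0.2 to 0.4, the typical shift is 2.5 points (12.6 × 0.2) to 6.7 points (16.8 × 0.4).

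**5. With stratified allocation.** Simulated permuted blocks of four within C. dif. strata (an illustrative block size, 40,000 runs), with every result known at randomisation, gave an arm difference of at most two positives. A difference of two occurred in about 8% of runs.

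**The case against.** The strongest objection is that chance imbalance under randomisation is not bias. It is part of the sampling variation that an unadjusted interval already covers. Against a standard error of about 16 points, a typical shift of 2.5 to 6.7 points is modest. This stands: the gain is in precision and in balance for the trial at hand, not in validity.

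A reader might also infer four stronger claims, which the documents do not support:

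- *That a material imbalance is likely.* At 9% to 32% for four or more positives, it is a real risk but well below even odds.
- *That a single unstratified sequence is in use.* The plan is silent on sequence generation. What can be said is that no stratification is described.
- *That C. dif. status is the main prognostic factor.* No cure rates by status are given. The documents show only that it determines treatment and defines analyses.
- *That status will be known when the envelope is opened.* The sample is sent on day 0, but the time of the result is not given, and the Intervention group section ties the enema to the time of diagnosis, which leaves room for a later result.

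Nor should the subgroup argument be pressed far. With eight positives, moving from 4:4 to 6:2 raises the standard error by about 15% (√(1/6 + 1/2) = 0.816 against √(1/4 + 1/4) = 0.707, equal variances). The main limit there is the size of the subset, which stratification does not change. It also does not settle what a pooled estimate over two different contrasts means.

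**Conclusion.** The point holds as a cheap improvement. A factor that sets treatment in both arms and defines separate analyses is not used in the described allocation or in the primary comparison. The risk of an arm difference of four or more positives is 8.8% to 31.5%, given equal arms of 18 and 6 to 16 positives. A four-patient difference is worth 4.4 to 8.9 points on the primary risk difference, against a 20-point margin and 81.3% power, given a 20 to 40 point gap in cure by status. The number of positives, the gap and the threshold of four are assumptions. If nearly all or nearly none of the patients are positive, the matter largely disappears. The stated sample size reproduces and is not in question here.

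**What to change.** 1. **Statistical plan.** State that the primary outcome is analysed stratified by, or adjusted for, C. dif. status from the day 0 sample, whenever that result is reported. A Mantel-Haenszel risk difference over the two strata is one option; it is on the scale used for the sample size. This step does not depend on how quickly the laboratory reports.

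2. **Procedures at baseline, Day 0.** Describe how the sequence is generated. Where the result is available by the evening of day 0, use two envelope sets with small random blocks: one for positive patients, and one for patients whose result is negative or pending. If stratification is already in place, saying so is enough for this step.

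**Cost.** A second envelope set and a few sentences of text; N stays at 36. Patients whose positive result comes late are allocated from the negative-or-pending set, so they are balanced only through the analysis. Allocation can be stratified only for patients not yet randomised; the analysis change can be fixed at any time before the outcome data are examined.

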## Control group:

- we will wait for spontaneus retreat of diarrhea, which is a standard of care.
- in the subset of patients with C. dif. positivity, the patients receive 250 mg of vancomycine every 6 hour (with rescue option of conversion to i.v. tigecycline).

# Intervention group :

- if considered safe, the patient receive Loperamide 2 mg p.o. 2 hours before FBT.
- FBT procedure 350 ml of thawed donor stool (stool suspension) will be delivered by retention enema in the patients colon. The patient will be positioned in left semilateral Trendelenburg's position for 15 minutes and then in right semilateral Trendelenburg's position for another 15 minutes. Faecal management system (e.g. FlexiSeal©) will be inserted and clamped for 2hours after FBT
- in all patients receiving FBT will be recorded body temperature, heart rate, oxygen saturation and blood pressure. 3hours after FBT blood culture will be taken.

- in the subset of patients with C. dif. positivity, 1 L normal saline enema will be performed at the time of CDI diagnosis and FBT will be repeated once more. No antibiotics will be administered (with rescue option of administration of i.v. tigecycline).

**FBT stool suspension** will be stored in specific –80°C freezer with connected alarm notification to guarantee continuous registration of the storage. Information on the FBT suspension labels includes donor code, suspension number, production and expiration date, volume, and storage temperature instruction. From each donor one of the sample will be store in freezer for the duration of the ongoing study.

The resulting faecal bacteriotherapy (FBT) preparation is defined as a mixture of 7 aliquots of processed stool intermediates from 7 donors.

The resulting graft will be drawn into four sterile 100 ml syringes and transferred to the ward where the recipient is hospitalized. Re-freezing of thawed or partially thawed extract is not permitted.

# Day 2, 3

Physical examination, SOFA score, evaluation of laboratory blood results (WBC, CRP, lactate, etc.) will be recorded as well as volume or frequency and consistency (Bristol scale) of stool. Concomitant medication and adverse events will be recorded.

#### Day 4

As above day 2,3 plus obtain stool + plasma samples, freeze -80 C

Day 5, 6

see Day 2, 3

Day 7

Primary outcome assessment (see below) followed by collection of plasma and faecal samples.

# Assessment of primary outcome:

An independent data analyst will retrospectively review the de-identified printouts of nursing notes from the two 12 hour shift day + night ending in the morning of day 7 and record the presence or absence of diarrhoea (defined as 3 or more stools per day or Bristol type 7 stool in the volume >300 ml/day if stool derivative device is inserted).

In case the patient is not on ICU, but remains at hospital, the research nurse will bring a special record form on day 6 and instruct both the patient and nursing staff to record during the next 24 hours the volume or frequency and consistency of stool using visual Bristol Scale and also to provide a sample of stool. In case the patient has been discharged, he/she will be contacted the day before over the phone by a research nurse and the next day the patient will be asked to bring the formulary and a stool sample to hospital of will be visited by a research staff at home.

Afterwards, as long as the patient remains on ICU, adverse events, antibiotic treatment, and stool volume/frequency are monitored daily.

Unique Protocol ID: 2021-002290-25 22.9.2021 Protocol version 9.2

In patients with faecal management device in place, follow up visits (identical to Day 4) are performed in 7 days interval up to day 28, and/or ICU discharge or FMD removal, whichever occurs earlier.

In patients who remain in ICU, but have had FMD removed, have the same follow up procedures, with the exception of stool sampling. Stool is collected and stored as close as practical to the day of the visit after the patient has had spontaneously defecated.

In patients who are not on ICU, but remain at hospital, will be visited by a research nurse at day 7, 14, 21 and 28 as long as they remain hospitalised. The visit will include monitoring of adverse event, notice on patient general status, the presence/absence of diarrhoea, antibiotic medication. Blood will be collected and frozen. Six month follow up is performed at follow up clinics and it includes history (incl. recent history of diarrhoea), physical exam and blood sampling. Patients willing to do so are requested to bring in a stool sample. Patients unwilling to show up will be interviewed over the phone.

	D0	D1	D2	D3	D4	D 5-6	D7	D14, 21, 28or D/C	6month follow up
ICF	х								
Review drug chart	Х								
Serum sample + freeze	х	x			х		x	x	х
Stool sample + freeze	х				х		х	(x)	х
Adverse events, Phys.exam, SOFA	х	х	х	х	х	х	х	х	
Blood culture		хх							
Primary outcome assessment							х		
in intervention group -FBT		х							

Unique Protocol ID: 2021-002290-25 22.9.2021 Protocol version 9.2

Table: Gantt diagram of study procedures. See text for details.

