# Primary end-point:

• Percentage of patients with treatment failure at day 7 after randomisation. Treatment failure is defined as either failure to administer allocated treatment for any reason or the presence of diarrhoea on day 7 after randomisation (as assessed by personnel blinded to treatment allocation).

22.9.2021 Protocol version 9.2

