## Method:

*Design*: prospective, randomised, controlled, parallel group, open-label, assessor blinded feasibility trial.

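### Blinded assessment of day-7 diarrhoea is promised for all patients but not secured: ICU notes are not stated to be masked for treatment, and no blinded reader is named off ICU

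*Combined protocol and SAP*

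**What the plan says.** The Primary end-point section counts a patient as a failure if the allocated treatment was not given or if diarrhoea is present on day 7, the latter "as assessed by personnel blinded to treatment allocation". The Method section calls the study an "open-label, assessor blinded feasibility trial". Neither statement makes an exception for patients who have left the ICU.

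Assessment of primary outcome then describes three routes:

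- **On ICU.** "An independent data analyst will retrospectively review the de-identified printouts of nursing notes", taken "from the two 12 hour shift day + night ending in the morning of day 7".
- **In hospital but off ICU.** A research nurse brings a form on day 6, and the task is to "instruct both the patient and nursing staff to record during the next 24 hours the volume or frequency and consistency of stool". The same section later has a research nurse visit ward patients on day 7 and note, among other things, whether diarrhoea is present and which antibiotics are being given.
- **Discharged.** After a telephone call the day before, "the patient will be asked to bring the formulary and a stool sample to hospital", or research staff visit at home.

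On what differs between arms, the Control group section says that in C. dif. positive patients "the patients receive 250 mg of vancomycine every 6 hour", with no duration given. The Intervention group section describes the enema, a faecal management system with no stated removal time, and one repeat FBT in C. dif. positive patients with no stated day. Monitoring of safety says that treating clinicians are not blinded.

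**The concern.** In an open-label trial, a blinded assessor is the main protection of this endpoint against detection bias. That protection depends on what the assessor can see and on whether every patient passes through that assessor.

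On ICU, the analyst is called independent and the notes de-identified. Neither word means that treatment is hidden. A nursing record of the last 24 hours may contain drug or procedure entries that point to the arm. Off ICU, the record comes from people who can know the allocation, and the text does not say who turns it into a yes or no for diarrhoea.

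The cut-offs (3 stools a day, or Bristol type 7 with more than 300 ml a day when a device is in place) leave room for borderline days. Each patient also carries a lot of weight in a trial of this size.

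**Working it through.** **Step 1. What is promised and what each route provides.**

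| Where the patient is on day 7 | Who records stools | Who classifies | Stated to be masked for treatment? |
|---|---|---|---|
| ICU | bedside nurses | independent analyst, from nursing notes | no; de-identified only |
| Ward | patient and ward staff; a research nurse also notes diarrhoea and antibiotics on day 7 | not stated | no |
| Discharged | patient, on a returned form | not stated | no |

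The promise covers all three rows. Only the first row names a classifier, and no row states that treatment information is removed. For ward patients, the text also does not say whether the form or the nurse's day-7 note decides the endpoint.

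**Step 2. Which clues can fall inside the ICU window.** The window is two 12-hour shifts, that is, the 24 hours ending on the morning of day 7.

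- First FBT: the study procedures table puts it on day 1, outside the window.
- Repeat FBT: C. dif. positive patients only, day not stated; it could fall inside the window, but nothing places it there.
- Vancomycin: 6-hourly in C. dif. positive controls, no duration stated, so it may be running in the window. It is not a perfect marker, because Monitoring of safety allows i.v. antibiotics in both groups.
- Faecal management system: described only in the FBT procedure, but the inclusion criteria already provide for a stool device before randomisation. It is at most a weak clue. The analyst must know device status anyway, because the definition uses a volume rule with a device and a stool count without one.

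So the arm may be revealed in some patients, mainly C. dif. positive ones. In C. dif. negative patients little is left beyond the device.

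**Step 3. The weight of one patient.** Inputs from Sample study size: success 45% on control and 66% on FBT, margin 20 points, one-sided 5%, power 80%, 36 patients allocated 1:1.

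The plan's own figure first:

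n per arm = (z0.95 + z0.80)² × [pC(1 − pC) + pF(1 − pF)] / (margin + pF − pC)²

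= (1.645 + 0.842)² × (0.2475 + 0.2244) / (0.20 + 0.21)²

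= 6.185 × 0.4719 / 0.1681 = 17.4, rounded up to 18 per arm, total 36. The stated size reproduces.

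Effect of reclassification at 18 per arm:

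- one patient in one arm: 1/18 = 5.6 points on that arm's rate, and the same on the difference;
- one patient in each arm, in opposite directions: 2/18 = 11.1 points on the difference;
- one patient in each arm, in the same direction: no change in the difference.

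The documents give no misclassification rate and no expected number of patients off ICU by day 7, so the arithmetic stops at the weight per patient.

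**The case against.** The strongest reply is that nothing here contradicts the promise. The Primary end-point section covers every patient, Assessment of primary outcome does not rule out a later blinded reading of ward and home forms, and the ICU route has an independent reader, de-identified papers and a fixed window. A reader might infer that blinded assessment is simply not delivered. The documents do not support that: they neither say that treatment entries stay in the printouts nor that the analyst knows the allocation.

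Other parts of the reply also stand:

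- The ICU clues are limited, as Step 2 shows. The protocol mentions the drug chart separately from the nursing notes, and whether the notes list drugs is not stated.
- The analyst applies numerical rules to recorded values; the Bristol type is scored at the bedside. The treatment-not-given part of the endpoint does not depend on this reading.
- Masking the analyst does not touch the larger route of bias, which is recording by staff and patients who can know the arm.
- Eligibility expects a stay of more than 7 days, so few patients may take the off-ICU routes. That use of these routes differs by arm would be speculation.
- A reader might also infer that two or three favourable readings would use up 11 to 17 of the 20 margin points. The arithmetic is right (2/18 and 3/18), but the number of such readings is assumed, as would be any misclassification rate behind a type I error figure.

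What does not stand is that this is only a missing detail. As written, the procedure gives the analyst nursing notes with no masking of treatment, and it uses a different route off ICU with no classifier named. A better method is available with the staff already planned.

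**Conclusion.** The point holds as a gap between promise and procedure: blinded assessment is stated for all patients but not secured. The off-ICU part is the firmer one, because no blinded reader is named there at all. The ICU part is a risk in some patients, not a demonstrated unblinding.

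The size is 5.6 points on an arm's rate per reclassified patient, assuming that all 18 per arm are analysed. The total effect cannot be derived, and the documents do not show that the result would be biased by any particular amount or in a particular direction. The change is worth making before unblinded data are read. It does not affect the sample size.

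**What to change.** In Assessment of primary outcome, have the existing independent analyst, stated to have no access to allocation, classify every patient: ICU, ward and discharged. The analyst should receive one standard stool-only extract with time, number, volume, Bristol type and device yes/no. The device item has to stay because the definition needs it. Remove drug, procedure and allocation text before the extract reaches the analyst. Send ward and home forms to the same analyst in the same format, and say that this classification, not the research nurse's day-7 note, decides the endpoint.

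In Primary end-point and Method, state that stool recording is open-label and only classification is blinded. Bias in bedside or patient recording then remains, and should be reported as a limitation.

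The cost is a short form and masking work by the study team, with no extra reader.

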## Study subjects:

- Inclusion Criteria: All of the following: Informed consent (see below), Age > 18 yrs., In-patient in ICU or HDU (incl. burn unit) and expected to stay for >7 days, Diarrhoea following antibiotic treatment defined as 3 or more stools per day or Bristol type 7 stool in the volume >300 ml/day if stool derivative device is in place, persisting for 24 hours despite enteral feeding formula has been stopped.
- Exclusion criteria: Death appears imminent or ceilings of care put in place, presence of new-onset sepsis defined as per 2016 definition, lactate >2.0 mM, colon diameter > 9 cm on plain AXR, the necessity of ongoing antibiotic treatment for another reasons. Unable to tolerate enema for any reason (e.g. surgery of the GI tract in the past year). Pregnant and lactating woman. Patients with a history of severe anaphylactic food allergy, any other reason

22.9.2021 Protocol version 9.2

which — as per judgement of the treating clinician — makes faecal transplantation unsafe or not feasible (Note: All screening failures based on this criterion will be reported separately, inc. the reason why it was considered unsafe or not feasible to proceed).

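### The rule for day-7 diarrhoea depends on a stool device that only the FBT procedure prescribes, and the assessor's notes may still show entries that point to the arm

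*Combined protocol and SAP*

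**What the plan says.** The primary end-point is treatment failure at day 7: either the allocated treatment was not given, or diarrhoea is present. The section *Primary end-point* requires the diarrhoea part to be judged by staff blinded to allocation.

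- **Scoring rule.** *Assessment of primary outcome* calls diarrhoea "defined as 3 or more stools per day or Bristol type 7 stool in the volume >300 ml/day if stool derivative device is inserted". The data come from "the two 12 hour shift day + night ending in the morning of day 7". An independent analyst reads printed nursing notes from which identifiers have been removed.
- **Device in the FBT arm.** *Intervention group* says that a faecal management system "will be inserted and clamped for 2hours after FBT". It gives no removal time.
- **Device in the control arm.** *Control group* prescribes none: "we will wait for spontaneus retreat of diarrhea, which is a standard of care".
- **Device in either arm.** The entry criteria in *Study subjects* already allow for "Bristol type 7 stool in the volume >300 ml/day if stool derivative device is in place". The follow-up rules in *Assessment of primary outcome* cover patients with a device in place and patients whose device has been removed.
- **Treatment entries.** In C. dif.-positive controls "the patients receive 250 mg of vancomycine every 6 hour", with no course length. In C. dif.-positive FBT patients "FBT will be repeated once more", with no day stated. The table of study procedures places the row "in intervention group -FBT" on day 1.
- **Analysis.** *Statistical plan* gives an unadjusted per-protocol comparison and a separate C. dif. analysis. It does not mention device status.

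**The concern.** A randomised comparison needs the outcome to mean the same thing in both arms. Here the measuring rule changes with the presence of a device, and the protocol makes that device part of one treatment and not of the other. If more FBT patients than controls still have a device in the day-7 window, more of them are judged by volume and fewer by count. Part of any difference in failure would then come from the measurement.

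The second issue is blinding. The trial is open-label, so the primary outcome relies on the assessor not knowing the arm. Removing a patient's identity from the notes does not by itself remove entries about treatment.

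Both issues touch only the diarrhoea part of the composite. Failure to administer treatment is unaffected.

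**Working it through.** **1. The plan's own figure.** *Sample study size* gives 36 patients at 1:1, cure of 45% and 66%, a 20-point margin, one-sided 5% and 80% power.

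n per arm = (1.645 + 0.842)² × [0.45 × 0.55 + 0.66 × 0.34] / (0.21 + 0.20)² = 6.185 × 0.4719 / 0.1681 = 17.4, rounded up to 18, so 36 in total. The figure reproduces and is not in dispute.

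**2. Which rule applies to whom.** Three sections bear on how the limbs combine.

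- *Assessment of primary outcome* joins count and volume by an *or*, and ties volume to a device being inserted.
- The daily visits (*Day 2, 3*) and the form for patients outside the ICU ask for either volume or frequency, together with consistency. This fits volume with a device and count without.
- *Monitoring of safety* asks for frequency, volume and character every 12 hours. This leaves open that both limbs exist for some patients.

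The most natural reading is volume with a device and count without. The outcome section does not say so, and it does not cover a device that is present for only part of the 24 hours.

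**3. Why the limb can matter.** Take two illustrative patients with Bristol type 7 stool (values chosen here, not from the documents):

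| Output in 24 h | Scored by count | Scored by volume |
|---|---|---|
| 250 ml in three motions | diarrhoea | no diarrhoea |
| 400 ml in two motions | no diarrhoea | diarrhoea |

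On the natural reading, disagreement can therefore go either way. If the count also applied with a device in, the device could only add a route to failure, and an excess of devices under FBT would work against FBT. No section says how motions are counted once a device is in place.

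**4. Form of the bias.** Let g be the FBT-minus-control difference in the share of patients with a device in the day-7 window. Let d be the net difference in the probability that the same patient is scored as failure by volume rather than by count. If d is the same in both arms, the shift in the difference between arms is g × d. With g = 0 it is zero. The documents give neither g nor d, so no value can be calculated from them.

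**5. Scale.** One patient in an arm of 18 is 1/18 = 5.6 points. The 20-point margin corresponds to 0.20 × 18 = 3.6 patients. Near the planned rates, failures would be about 6/18 under FBT and 10/18 in controls. With the unpooled normal approximation, the one-sided 95% upper limit for the difference is:

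−0.222 + 1.645 × √(0.333 × 0.667/18 + 0.556 × 0.444/18) = −0.222 + 0.266 = 4.3 points.

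Moving FBT patients to failure one at a time gives 10.3 points (7/18), 16.1 (8/18) and 21.8 (9/18). Three net reclassifications would be needed to cross 20 points. This uses the non-inferiority rule in *Sample study size*. *Statistical plan* instead names a hazard ratio and states no margin.

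**6. What the assessor can see.** The window is the 24 hours ending on the morning of day 7, so the day-1 FBT lies outside it. The vancomycin course has no stated length and the repeat FBT has no stated day, so either could fall inside it in C. dif.-positive patients. No section says that treatment entries are removed from the printouts.

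**The case against.** The case against is substantial, and most of it limits the point.

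- **No imbalance is documented.** The device belongs to a day-1 procedure with a 2-hour clamp, devices may be present at entry in either arm, and removal is foreseen. This stands. A reader might infer that FBT patients will mostly be scored by volume and controls by count. The documents do not support that.
- **The limbs are nearly settled.** The wording favours volume with a device and count without. This stands as the likelier reading. A sentence stating it would be only a clarification, and it would leave part-window use and any imbalance untouched.
- **The size cannot be calculated.** This stands. Any loss of power or inflation of error would rest wholly on assumed values for g and d, so none is given here.
- **Device status on day 7 arises after randomisation.** A device may remain because diarrhoea persists, so an imbalance could reflect a treatment effect. This stands, and limits how a table by arm can be read.
- **The blinding clues are weak.** They concern mainly the C. dif.-positive subset. *Monitoring of safety* allows i.v. antibiotics, including vancomycin, in both arms, although the abstract gives the control treatment by mouth. Whether nursing printouts show drugs is unknown, and a threshold on count or volume leaves limited room for judgement. A reader might infer that the assessor is unblinded. The documents show only that this is possible.

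What survives is that, with the plan followed as written, the primary outcome can be measured by a different rule in each arm and the assessor can be shown the arm. Cheap safeguards exist against both.

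**Conclusion.** The point holds in conditional form. The scoring rule depends on a device that only the FBT procedure prescribes. The plan does not say how part-window use is scored, and its only stated means of blinding is the removal of identifiers.

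Size and direction are unknown, and the measurement effect is zero if device use in the day-7 window is balanced. The firm scale is 5.6 points per patient in an arm of 18. The documents do not support a claim that the outcome is biased toward either arm, nor that the problem would stay hidden: device status will be known, because follow-up visits depend on it. What is missing is a planned report of it by arm. The changes should be made before outcomes are scored, since a rule chosen after seeing the data could itself introduce bias. Confidence is medium.

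**What to change.** Keep the thresholds, device use, patient care and sample size as they are.

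1. Before scoring, state which limb applies when a device is in place, and how a device present for part of the 24-hour window is scored.
2. Give the blinded assessor a stool-only extract for that window: count, volume, Bristol type, and device status only as far as scoring needs it. Existing staff can prepare it, with FBT, enema and drug entries removed.
3. Report device status in the window by arm, descriptively. Note that it is a post-randomisation variable and may reflect persisting diarrhoea.
4. Add a sensitivity analysis that scores patients whose result depends on the limb used, or on a limb that was not recorded, first as failure and then as success. Where both limbs are recorded, also apply one common rule to all such patients.

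The cost is a little extraction and analysis work. Two limits remain. Device entries kept for scoring may still hint at the arm, although a device is not specific to FBT. The common-rule analysis may cover few patients if most have only one limb recorded.
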